7.4 Measurements

7.4.1 Weight: will be measured at each in-person visit, at approximately the same time of day. The weights are obtained at baseline, week 9 and at the end of study. The ideal weight measurement should be obtained within 7 days of completing the 8 weeks and 6 months behavioral intervention. However, to accommodate participants who may not be able to meet within this window, the weight measurement can be obtained within 14 days of these time points. Weight in light indoor clothes without shoes will be recorded by any trained, certified staff using a high-quality digital scale in any of our Johns Hopkins Medical Institute (JHMI) clinics. Duplicate measurements will be made to ensure accuracy. Weight will be measured in pounds for ease of interpretation by the participants and subsequently converted to kilograms for data analysis. Scales will be calibrated per the Sidney Kimmel Comprehensive Cancer Center's (SKCCC) standards. The engineering department or study staff will perform quarterly calibration checks by using standard weights. The weight at SV will be used to determine eligibility. Measurements will be repeated once, if difference between the two measurements is more than 0.1 kg, measurement will be repeated until difference between two measurements is less than 0.1 kg.

7.4.2 Height: to the nearest 0.1 cm will be measured once at any of our JHMI clinics. The participant stands shoeless on a firm, level surface, with her head in the horizontal (Frankfort) plane. Measurements will be repeated once, if difference between the two measurements is more than 1 cm, measurement will be repeated until difference between two measurements is less than 1 cm.

7.4.3 BMI: will be calculated as the Quetelet index (kg/m²)

NOTE: All physical measurements should be taken by a member of the study team or an appropriate clinical employee (e.g., clinical associate who regularly collects physical measurements).

7.4.4 Daily steps: are measured by Fitbit. Fitbit devices use a 3-axis Fitbit to understand your motions. An Fitbit is a device that turns movement (acceleration) into digital measurements (data) when attached to the body.

7.4.5 Intensity of physical activity (also known as MVPA, which is moderate to vigorous physical activity): is measured by the Godin Leisure-Time Exercise Questionnaire. Leisure-time physical activity is an important subtype of physical activity (PA) for research and behavior change intervention in oncology context. This is a 3-item self-administered questionnaire with the first three questions seeking information on the number of times one engages in mild, moderate and vigorous PA bouts of at least 15 min duration in a typical week. Examples of PA are provided for each intensity category. Scores derived from the questionnaire include total weekly PA, called a Leisure Score Index (LSI), in which number of bouts at each intensity is multiplied by 3, 5, and 9 metabolic equivalents (METs) and summed. LSI scores can be used for ranking individuals from the lowest to highest PA levels. In addition, the score obtained from MVPA can be used to classify respondents into *active* and *insufficiently active* categories according to published PA guidelines for cancer survivors.

7.5 Questionnaires

7.5.1 Clinical and Demographic Information

The designated research coordinator(s) participating in this project will enter clinical information associated with each participant in the database. Such data could include, but is not limited to: medical record number, age, sex, physical measurements, treatment history, tumor size, tumor grade, tumor receptor status, pathology report, smoking history. Such information will be retrieved from existing clinical databases (e.g., Johns Hopkins Electronic Patient Record) and patient questioning.

Participants will be asked to provide contact information for their other health care providers in case information needed is not contained in the Hopkins clinical databases, or if the participant assumes care outside the institution. In addition, participants may be reached by phone to help with any questions or clarifications, or additional follow-up requirements.

Participants will also be asked about current medications at each visit. This will be documented in the electronic medical record.

7.5.2 Patient Reported Outcomes

We will collect PROs using REDCap, which is already in throughout the institution by several clinical investigations. PROs will include questionnaires regarding physical function, pain, fatigue, mental well-being, endocrine symptoms, sleep, sexual function, and medication adherence, at baseline, 2, and 6 months following initiation of the intervention. Pain, fatigue, mental well-being, sleep, and physical function will be assessed using the NIH PROMIS questionnaire; endocrine symptoms with the FACT-endocrine symptoms, and sexual function

with the MOS-Sexual Function. Medication adherence will be monitored with the institutional drug diary.

Enrolled patients will be given a letter with a username and password for the Fitbit website, and will be oriented on how to use the website; an email address will also be recorded for each participant. Participants will receive e-mail reminders when it is time for them to complete the REDCap questionnaire. They will be encouraged to complete the questionnaire prior to any planned clinic visit; however, they will be informed that a research coordinator can assist them prior to their visit if they prefer to complete the questionnaire at the clinic. Whether patients complete the PRO questionnaire at home or in the clinic, they will access the questionnaires via the internet. At follow-up clinic visits for patients who completed the PRO questionnaires, clinician sub-investigators will have a summary report available to them via REDCap.

Questionnaires will focus on some basic background information and patient reported outcomes, with more detailed survey information as follows. Data from the questionnaires will be available for export into spreadsheets or other tools for analysis.

NOTE: In the event that questionnaires through REDCap are not available, we will use paper-based questionnaires.

The questions that will be included in the REDCap system are included in Appendix E. Score interpretation is in Appendix F. Domains that will be included in REDCap are as follows:

- General health and physical function will be assessed using NIH PROMIS Adult Physical Function Short Form 1¹⁰². The physical function item bank measures self-reported capability rather than actual performance of physical activities, and generally includes the functioning of one's upper extremities (dexterity), lower extremities (walking or mobility), and central regions (neck, back), as well as instrumental activities of daily living, such as running errands. A single physical function capability score is obtained from a short form, and has been validated in adults with chronic illnesses.
- Pain will be assessed using the NIH Patient-Reported Outcome Measurement Information System (PROMIS) adult pain interference version 1.0 short form. The pain interference item bank measures the self-reported consequences of pain on various aspects of daily life. This includes the extent to which pain hinders involvement in social, cognitive, emotional, physical, and recreational activities. The short form is comprised of 6 questions which assess pain interference over the previous seven days. Each question has five response options ranging in value from one to five. A total raw score is calculated by summing the values of the response to each question, and then translated into a T-score using a conversion table. The T-score rescales the raw score into a standardized score with a mean of 50 and a standard deviation (SD) of 10. Therefore, a person who has a T-score of 40 is one SD below the U.S. general population mean. Reliability and validity have been previously reported 103.
- Fatigue will be measured using the NIH PROMIS Adult Fatigue Version 1.0 short form. The NIH fatigue question bank evaluates a range of self-reported symptoms, from mild subjective feelings of tiredness to an overwhelming, debilitating, and sustained sense of exhaustion that likely decreases one's ability to execute daily activities and function. Fatigue is divided into the experience of fatigue (frequency, duration, and intensity) and

the impact of fatigue on physical, mental, and social activities. The short form used has 7 questions which assess fatigue over the past seven days. As with all of the PROMIS short forms, each question has five response options ranging in value from one to five. A total raw score is calculated by summing the values of the response to each question, and then translated into a T-score using a conversion table. The T-score rescales the raw score into a standardized score with a mean of 50 and a standard deviation (SD) of 10. Therefore, a person who has a T-score of 40 is one SD below the U.S. general population mean. Reliability and validity of the fatigue assessment in cancer patients has been reported 104.

- Mental health will be evaluated using the NIH PROMIS Depression and Anxiety questionnaires. The Adult Depression Version 1.0 Short Form is an 8 question survey, and the Adult Anxiety Version 1.0 Short Form is a 7-item survey, for a total of 15 mental health questions. The depression item bank assesses self-reported negative mood (sadness, guilt), views of self-criticism, worthlessness), and social cognition (loneliness, interpersonal alienation), as well as decreased positive affect and engagement (loss of interest, meaning, and purpose). The anxiety item bank measures self-reported fear (fearfulness, panic), anxious misery (worry, dread), hyperarousal (tension, nervousness, restlessness), and somatic symptoms related to arousal (racing heart, dizziness). The anxiety and depression scores are calculated individually, in the same way all PROMIS scores are calculated as above.
- Endocrine symptoms will be assessed using the endocrine subscale of the Functional Assessment of Cancer Therapy-Endocrine Symptom questionnaire. The Endocrine Subscale was designed for use with the FACT-B (Functional Assessment of Cancer Therapy for breast cancer patients) but has been tested on its own¹⁰⁵. It comprises 18 items in which patients indicate how true a statement has been for them over the prior 7 days using a 5-point scale.
- Disturbance in sleep or sleep changes on therapy will be evaluated with the NIH PROMIS Adult Sleep Disturbance Version 1.0 Short Form. The sleep disturbance item bank assesses self-reported perceptions of sleep quality, sleep depth, and restoration associated with sleep over the 7 days before questionnaire administration. This includes perceived difficulties and concerns with getting to sleep or staying asleep, as well as perceptions of the adequacy of and satisfaction with sleep¹⁰⁶.
- Changes in sexual function will be evaluated using the MOS Sexual Functioning Scale, which consists of four items assessing interest in sex, ability to relax and enjoy sex, arousal, and ability to have an orgasm. Items are rated on a 5-point scale (1=not a problem, 2=little of a problem, 3=somewhat of a problem, 4=very much of a problem, and 5=not applicable). This scale is useful for measuring sexual function in both men and women. It has demonstrated good reliability and construct validity in breast cancer patients 107.
- Medication adherence will be assessed using the institutional drug diary (APPENDIX G).

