4.2 Secondary Objectives

- 4.2.1 To compare cardiometabolic biomarkers (HbA1c, IGF 1, fasting glucose, fasting lipids, fasting insulin, adiponectin and leptin levels), microbiome composition, body composition, and PROs at 2 and 6 months to baseline levels among SLOW-BWL who achieve ≥5% weight loss.
- 4.2.2 To compare cardiometabolic biomarkers, microbiome composition, body composition, and PROs at baseline of SLOW-BWL women who achieve ≥5% weight loss versus the SLOW-BWL women who do not achieve 5% weight loss.
- 4.2.3 To compare the moderate to vigorous physical activity (MVPA) and daily steps at 2 and 6 months to baseline levels among SLOW-BWL who achieved ≥5% weight loss vs the SLOW-BWL who did not achieve 5% weight loss.

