APPENDIX C: Weekly weight and symptom survey

During the behavioral intervention, coaches call patients weekly the first 3 months, followed by monthly for months 4-6. Patients will receive a REDCap survey on a weekly basis with the following question:

1) What is your v	weight this week?
*If patients have not o	completed this survey before the call with the coach, the coach may enter
the data that is conve	yed verbally.

During months 3-6, ALL study participants will continue with weekly survey, in addition to a question about any new symptoms:

2) During the past 7 days, have you experienced any new symptoms (such as abdominal pain, anxiety, constipation, diarrhea, dizziness, dry mouth, fatigue, gastroenteritis, headache, hot flush, insomnia, nausea, tremor, vomiting etc.)?

^{*}If patients have not completed this survey before the call with the coach, the coach may enter the data that is conveyed verbally.

^{**}The coordinator will review all new symptom entries in the REDCap survey on a weekly basis, and new symptoms will be reported to the PI for further evaluation.

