 - b. Rarely
 - c. Sometimes
 - d. Often
 - e. Always
- 7. How often did you have enough energy to exercise strenuously?
 - a. Never
 - b. Rarely
 - c. Sometimes
 - d. Often
 - e. Always

X. Patient Reported Outcomes (PROs) – MOS Sexual Function Scale

	Not a	Little of a	Somewhat of a	Very much of	Not
Lack of sexual	problem	problem	problem	a problem	applicable
interest					
	1	2	3	4	5

Unable to relax and enjoy sex			Somewhat of a problem	•	Not applicable
enjoy sex	1	2	3	4	5
Difficulty in becoming sexually	Not a problem	Little of a problem	Somewhat of a problem	•	Not applicable
aroused	1	2	3	4	5
Difficulty in having an orgasm			Somewhat of a problem	•	Not applicable
un organii	1	2	3	4	5

XI. Patient Reported Outcomes (PROs) – Endocrine Symptoms FACT-ES

Please mark one number per line to indicate your response as it applies to the past 7 days.

	Not at all	A little bit		-	Very much
I have hot flashes	0	1	2	3	4
I have cold sweats	0	1	2	3	4
I have night sweats	0	1	2	3	4
I have vaginal discharge	0	1	2	3	4

I have vaginal itching/irritation	0	1	2	3	4
I have vaginal bleeding or spotting	0	1	2	3	4
I have vaginal dryness	0	1	2	3	4
I have pain or discomfort with intercourse	0	1	2	3	4
I have lost interest in sex	0	1	2	3	4
I have gained weight	0	1	2	3	4
I feel lightheaded (dizzy)	0	1	2	3	4
I have been vomiting	0	1	2	3	4
I have diarrhea (diarrhea)	0	1	2	3	4
I get headaches	0	1	2	3	4
I feel bloated	0	1	2	3	4
I have breast sensitivity/tenderness	0	1	2	3	4

I have mood swings	0	1	2	3	4
I am irritable	0	1	2	3	4
I have pain in my joints	0	1	2	3	4

XII. Godin Leisure-Time Exercise questionnaire

Please indicate the average amount of exercise you did in the last 7 days.

When answering these questions, please:

- note that the main difference between the 3 questions below is the intensity of the exercise.
- if you did not do any exercise in one of the categories, please write in "0".

Considering a typical week (7 days), how many times on average did you do the following kinds of exercise for more than 15 minutes during your free time?

For example, if you did fast walking for a total of 60 minutes over the past week, you would write 4.

	Times Per Week
STRENUOUS EXERCISE	
What is strenuous? HEART BEATS RAPII (e.g. running, jogging, hockey, soccer, squa swimming, vigorous long distance bicycling	sh, cross country skiing, vigorous
	Times Per Week
MODERATE EXERCISE	
What is moderate? NOT EXHAUSTING, I	•
What is moderate. NOT EXTROSTING, E	IGHT PERSPIRATION

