- Surveys were validated in the general population.
- All of these domains are mapped to a mean score of 50, with a standard deviation of 10.
- Highlighted scores represent a score more than 2 standard deviations from the mean (20 points) or a worsening of at least half a standard deviation (5 points).

Sexual Function:

- This survey was validated in patients with major medical problems with and without depression, and patients without medical problems but with depression.
- For this population, the mean sexual problem scores ranged from 24.48 43.5, with a standard deviation of 32.
- Highlighted scores represent a score that is worse than the average scores among an ill population (40 points) or a worsening of at least half a standard deviation (16 points).

Endocrine Symptoms:

- This survey was validated in female breast cancer patients undergoing a variety of hormone therapies as well as normal controls.
- This survey is mapped to a mean score of 59.7, which is the total group mean from the validated population, with a standard deviation of 9.2.
- Highlighted scores represent a score that is two standard deviations away from the mean (41.3 points) or a worsening of at least half a standard deviation (4.6 points).

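### The endocrine-symptom score contains a weight-gain item, so part of any improvement linked to weight loss may be weight change itself; report it with and without that item

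*Combined protocol and SAP*

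**What the plan says.** Section 7.5.2 counts endocrine symptoms among the patient-reported outcomes (PROs) and names the instrument: "Endocrine symptoms will be assessed using the endocrine subscale of the Functional Assessment of Cancer Therapy-Endocrine Symptom questionnaire". It describes the recall period and length as follows: "It comprises 18 items in which patients indicate how true a statement has been for them over the prior 7 days".

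Appendix E, part XI, prints the items, each scored 0 to 4. One is "I have gained weight". Others include "I feel lightheaded (dizzy)" and "I have been vomiting", as well as diarrhea, headaches and hot flashes.

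Appendix F interprets the endocrine score only as a total, with higher scores better. The expected range is 41.3 to 76, the mean 59.7 and the SD 9.2. It flags "a worsening of at least half a standard deviation (4.6 points)".

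Section 3 hypothesises that, in SLOW-BWL, losing at least 5% of baseline weight goes with improved PROs. Objective 4.2.1 compares "PROs at 2 and 6 months to baseline levels among SLOW-BWL who achieve" that loss. Section 13.2 compares outcomes over time and between SLOW-BWL women above and below 5%. It plans no item-level analysis and no version of this score without the weight item.

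**The concern.** The analyses group or select women by weight loss, and one item of the outcome asks about weight gain. Where that item stands above zero at baseline, it can fall in women who lose weight even if hot flashes, vaginal symptoms, mood and joint pain stay as they were. A gain in the total could then be reported as relief of endocrine symptoms when part of it restates the grouping variable. Without a prespecified version that omits the item, the choice of score would be made after the data are seen.

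**Working it through.** **1. Reproduce the plan's figures.**
- Lower end of the expected range: 59.7 − 2 × 9.2 = 41.3, as stated.
- Flagged change: 9.2 / 2 = 4.6, as stated.
- Maximum: Appendix E prints 19 items, and 19 × 4 = 76, the top of the Appendix F range. Section 7.5.2 says 18 items, which would give 72. The 76-point maximum therefore needs all 19 printed items, including the weight item.

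**2. Upper bound for the weight item.** It can move the total by at most 4 points: 4 / 76 = 5.3% of the scale, 4 / 9.2 = 0.43 SD, and 4 / 4.6 = 87% of the flag. This is a ceiling for one woman, not an expected mean shift.

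**3. Plausible mean shift.** The documents give no baseline distribution for the item, so the mean fall d in achievers is an assumption: 0.25 to 0.5 if most women start near zero, 0.9 to 1.7 if the baseline mean is around the middle of the item's range.

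**4. Effect on the paired test in objective 4.2.1.** Inputs:
- Number of achievers: section 13.1 plans about 30 SLOW-BWL women and a target rate of 29%. 30 × 0.29 = 8.7, so n = 9.
- Assumed: the other items change by 0 on average, with SD s = 3, 5 or 7 for their sum.
- Assumed: the weight item's change has SD 1 and is independent of the rest.

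The two-sided 5% paired t-test has 8 degrees of freedom and noncentrality d × √9 / √(s² + 1). At the extremes:
- d = 0.25, s = 7: 0.25 × 3 / √50 = 0.11, rejection 5%.
- d = 1.7, s = 3: 1.7 × 3 / √10 = 1.61, rejection 30%.

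| Mean fall d | d / 4.6 | s = 3 | s = 5 | s = 7 |
|---|---|---|---|---|
| 0.25 | 5% | 6% | 5% | 5% |
| 0.5 | 11% | 7% | 6% | 5% |
| 0.9 | 20% | 12% | 8% | 6% |
| 1.7 | 37% | 30% | 14% | 10% |

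Without the item, the mean change is 0 under these assumptions and the test rejects at its nominal 5%.

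**5. Items shared with Contrave symptoms.** Section 10.2.6 gives NB32 rates of 13% for headache, 9% for dizziness and 9% for vomiting. If each affected woman worsens by k points on that item, the mean shift is k × (0.13 + 0.09 + 0.09) = 0.31k. For an assumed k of 1 to 4, that is 0.3 to 1.2 points, or 0.03 to 0.13 SD, with no subtraction for background rates.

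**The case against.** **The item has a 7-day recall.** It asks about recent gain, not about loss since enrolment. A woman whose weight was stable at entry can score 0 and then has no room to improve, and nothing in sections 6.1 or 6.2 requires recent gain. This stands. A reader might infer that the score must improve in every woman who loses weight; the documents do not support that. It is why the lower rows of assumed falls belong in the range, and there the inflation is negligible.

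**This is one secondary PRO.** Section 5.10 makes physical function the primary PRO and speaks only of modulation for the others. Section 13.2 does not name the endocrine score, so its analysis as a total is inferred from Appendix F, the only scoring given. This also stands, and limits the weight of the point.

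**Larger error rates do not apply.** Pooling all 6-month achievers, FAST and SLOW, would give more women and higher rejection rates, but no objective names that analysis of PRO change. Objective 4.2.2 compares achievers and non-achievers on PROs at baseline only, so a comparison of change between them rests on the general wording of section 13.2.

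**Drug side effects.** A reader might infer that Contrave symptoms make the score uninterpretable, because Appendix C lists "constipation, diarrhea, dizziness, dry mouth, fatigue, gastroenteritis, headache, hot flush" and others. The documents do not support going that far. The likely shift is small (step 5). Contrave starts at week 9, so it matters mainly at 6 months. Symptoms are also recorded separately, in the weekly survey, the drug diary and the adverse-event forms. Hot flashes are a core endocrine symptom, and removing them would damage the scale.

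**Conclusion.** The point holds for the weight item. The outcome partly contains the variable used to group the women, and no planned analysis separates the two. The overlap can affect both the 2-month and the 6-month comparisons with baseline.

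Its size is uncertain. Over assumed mean falls of 0.25 to 1.7 points, the shift is about 5 to 37% of the 4.6-point flag, and a nominal 5% paired test in about 9 SLOW-BWL achievers rejects in roughly 5 to 30% of trials. The upper end needs both a high baseline on the item and little variation in the other items. Neither is documented.

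This is a low-cost improvement to one secondary PRO. It does not touch the primary endpoint, the two-stage design or the physical function outcome.

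**What to change.** Add to section 13.2:
- Analyses relating endocrine symptoms to weight loss are reported for the full score and for the score without the weight-gain item.
- A gain seen only in the full score is not interpreted as endocrine-symptom benefit.

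The items that overlap with listed Contrave symptoms (headache, dizziness, vomiting, diarrhea) may be tabulated descriptively at 6 months. They should stay in the score and should not be a condition for interpreting it.

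The item count in section 7.5.2 (18) should be reconciled with Appendix E (19) and the 76-point maximum in Appendix F, so that it is clear which items the full score contains.

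Cost: two sentences and one rerun on data already collected. The downside is that the shortened score has no norm or flag in Appendix F, so the full score remains in the report.
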